### **9.2 Exclusion Criteria:**

- 1) 17 years of age or younger;
- 2) Not male gender;
- 3) 0 male sex partners in the prior year;
- 4) No diagnosis of HIV and/or not currently prescribed ART;
- 5) No self-reported detectable VL in past 12 months OR self-reported very good/excellent HIV medication adherence;
- 6) Residing outside of the New York City metropolitan area and/or no availability meet with project staff at each assessment time point; and
- 7) Non-English-speaking (since the intervention will be in English).

### **9.3 Screening:**

Persons interested in the study will be scheduled for an in-person appointment at CHEST to complete the screener items, baseline VL blood draw, and urine samples for drug use. Those that meet the inclusion criteria and do not meet the exclusion criteria will be guided through the consent process and randomized.

## **10.0 Vulnerable Populations**

### **10.1 Vulnerable Populations: *Identify which of the following populations will be involved in this study. (You may not include members of the populations***

*below as participants in your research unless you indicate this in your inclusion criteria above.)*

- Children
- Pregnant women/Fetuses/Neonates
- Prisoners
- Adults lacking capacity to consent and/or adults with diminished capacity to consent, including, but not limited to, those with acute medical conditions, psychiatric disorders, neurologic disorders, developmental disorders, and behavioral disorders
- Non-English speakers
- Those unable to read (illiterate)
- Employees of the researcher
- Students of the researcher
- None of the above

*10.2 Adults lacking capacity to consent and/or adults with diminished capacity to consent:*

*N/A*

*10.3 Additional Safeguards:*

*N/A*

## **11.0 Number of Participants**

*11.1 Number of Participants to be Consented:*

410

## **12.0 Recruitment Methods**

*12.1 Recruitment Process:*

In order to recruit at least 20 eligible men per month during the full randomized controlled trial, research staff at CHEST will use multiple approaches, all coordinated by the Director of Recruitment who has several years of experience recruiting MSM for RCTs at CHEST. First, two recruiters will be utilized for active field-based recruitment efforts. They will target venues such as gay bars, community events, and HIV clinic settings. Potential participants will be given project related materials, and can call later for an appointment, provide contact information for a CHEST staff member to call them to schedule the in-person baseline visit, or schedule the appointment at the time of recruitment, depending on the venue and interests of the participant. Rigorous efforts will be undertaken to ensure that recruitment staff maintain adherence to the study protocols, and recruiters receive extensive training in how to approach potential participants and follow strict written guidelines regarding ethics and

**PROTOCOL TITLE: A Technology-Delivered Peer-to-Peer Support ART Adherence**

**Intervention for Substance-using HIV+ Adults**

**VERSION DATE: 4/2/18**

professional conduct. All recruitment images and text for flyers, palm cards, and online banner ads are attached (Recruitment Materials).

Recruiters work in pairs to ensure their safety and adherence to protocol. Recruiters utilize palm cards with information about the study, and conduct on-site preliminary screening via iPads. After each recruitment shift, recruiters complete a report to facilitate the overall monitoring of the recruitment process. Second, a passive recruitment strategy through advertising will be developed by our consultant, who has been leading marketing efforts for intervention trials at CHEST for over ten years. Advertisements will be run in publications targeting MSM in NYC, brochures will be developed for distribution at HIV clinics and AIDS service organizations, and online recruitment will be conducted via Facebook postings.

Men recruited for usability testing will be recruited using similar methods as described above.

**12.2 Source of Participants:**

Participants will be recruited through a combination of the active and passive recruitment strategies described above, both from the community and from CHEST's network.

**12.3 Identification of Potential Participants:**

Participants will self-identify in response to banner ads, flyers, or targeted outreach by CHEST recruiters.

**12.4 Recruitment Materials:**

Recruitment materials will include palm cards, flyers, and web ads, samples of which are attached.

**12.5 Payment:**

Participants will be offered \$50 in cash for every study visit at baseline, 6-month, and 12-month follow-up. In addition, we will offer a \$25 Amazon gift card raffle each week for participants who engage with the TWM intervention in a weekly basis. Thus, participants could possibly earn up to \$750 if they won the raffle each time (which is highly unlikely). However, realistically, participants will earn \$200 for completing the assessments and possibly a \$25 Amazon raffle if they are chosen in a given week. Raffle winners will receive their gift card code via email.

Participants in the usability testing group will be given \$50 cash at each study visit, baseline and follow-up interview. Payment to subjects will be made during each visit (baseline, 6-month, and 12-month follow-up) and will be administered by CHEST staff. Each study visit will provide the opportunity to earn \$50 and therefore the payment will not be prorated.

Subjects will be paid during each assessment period and therefore participants will be paid only for those assessments they present for. If a participant has elected to continue to participate in the study after moving out of the study area, payment for follow-up visits will be sent by electronic Amazon gift card.

## 13.0 Withdrawal of Participants

### 13.1 Withdrawal Circumstances:

Due to its social nature the intervention website will be monitored regularly by study staff. If a participant is found to be behaving in an inappropriate or abusive manner, or is not acting in accordance with the community guidelines established on the site, the study coordinator will reach out to the individual about modifying their behavior. If an individual continues to disrupt the experiences of other participants they may be withdrawn from the site. Participants may also choose to withdraw themselves from study participation at any time.

### 13.2 Withdrawal Procedures:

When a participant is withdrawn for any reason, data collection will cease and no further follow-up will occur. For control participants, CHEST staff will record the reason for their withdrawal and remove them from the email list for the control emails and cease follow-up. For intervention participants, CHEST will record the reason for their withdrawal and cease follow-up, and UMN staff will terminate the participant's access to the TWM site. Data that has been already collected will be deleted at the request of the participant.

### 13.3 N/A

## 14.0 Risks to Participants

### 14.1 Foreseeable Risks:

We identified the following 6 items as possible risks to subjects:

- 1) By misspelling a web address or “surfing” the net, some individuals may unintentionally go to the study website. We deem this unlikely as we will use the prefix “https:” to prohibit persons from coincidentally viewing the site, and we intend to recruit from a website that is explicitly for HIV-related information. Nonetheless, if someone were to mistakenly view the study website home page, we anticipate that the information contained on the homepage will be benign to viewers.
- 2) Potential participants or participants enrolled in the study may have concerns about others finding out about their HIV status or other personal behavior (e.g., sexual behavior). We anticipate that the likelihood of this occurring is high given that a major feature of the intervention is for participants to network with one another and that eligibility for enrollment in the study requires participants to identify as

a HIV+. Subjects will be informed during the consent process of the basic features of the intervention and those who are not comfortable interacting with other HIV+ persons will be encouraged to not participate in the study. Those who do enroll will be given the option of utilizing intervention features with which they feel comfortable, although utilization of all features will be encouraged.

- 3) Participants may feel discomfort in answering personal questions during the assessments and/or revealing aspects of themselves during the intervention period with other participants. Similar to #2 above, the nature of the assessment and intervention is such that participants will be encouraged to provide personal information about themselves and therefore the likelihood of this occurring is high. During the assessments, participants will be given the option to choose a “refuse to answer” response, and, during the intervention, participants can divulge as little or much about their personal history as they choose. We anticipate that these steps will ensure that risk to the participant is minimized to his comfort level.
- 4) Participants may receive hostile communications or incorrect information from other participants during the course of the intervention. It is possible that some participants may respond aggressively or with hostility to other participants. Likewise, although well-intended, participants may provide inaccurate information about adherence or its risk factors to other participants by interactions through the website message boards/social networking wall.
- 5) Participants may be concerned about the security of their data, particularly since it is collected and stored electronically. Our study team has significant experience developing security protocols for Internet-based studies, and we will take a variety of steps to ensure participant security, including using a dedicated server behind a firewall, encryption of data, separation of identifiers from responses, and password-protected access to data. Therefore, we believe that this risk will be minimal.
- 6) Discomfort or infection due to phlebotomy.

#### *14.2 Reproduction Risks:*

*N/A*

#### *14.3 Risks to Others:*

*N/A*

### **15.0 Incomplete Disclosure or Deception**

#### *15.1 Incomplete Disclosure or Deception:*

*N/A*

### **16.0 Potential Benefits to Participants**

#### *16.1 Potential Benefits:*

Potential Benefits. Participation in the TWM arm may provide participants with information and exercises that help them build peer social support, monitor their medication adherence and HIV-related care appointments, and develop skills. Participants in the control group may gain basic knowledge about medication adherence and links to outside resources. In either the experimental or control condition, the primary benefit is access to health information that may assist participants to improve adherence and quality of life. Secondary benefits include positive feelings related to having assisted in the development and testing of a novel Internet-based adherence intervention, and if proven effective, the future availability of this intervention to others.

We will investigate whether there is greater benefit from the TWM intervention for drug-using participants compared to non-drug-using participants. We will use the approach described above with the two additional factors, self-reported current (past 5 months) drug use and the interaction with intervention (and time). In a similar manner, we will conduct exploratory analyses to identify other baseline participant risk groups for which the intervention is most beneficial. In addition, for participants in the TWM intervention, we will examine the effect of type and amount of intervention exposure (i.e., which component usage are related to outcomes) on improvement in ART adherence. All models will be altered and examined for robustness to specification.

#### 17.2 Power Analysis:

With N=400 (200 I, 200 C) and baseline undetectability of approximately 60%, at any single time point are powered to detect an approximately 14% difference in detectability. If both groups have approximately 60% undetectability at baseline, and we assume that the Intervention group will sustain that going forward, we could detect a difference of 14% undetectability at 5 months. Specifically, 60% undetectability in the Intervention group and 46% undetectability in the Control group at 5 months.

#### 17.3 Data Integrity: *N/A*

### 18.0 Confidentiality

#### 18.1 Data Security:

In this study, all paper consent forms will be stored at CHEST in a locked file cabinet in [name] office. All other paper documents will be stored in a filing cabinet used by the study team, and thus accessible to all the investigators. Original documents about subjects that could identify a subject will be kept in a separate locked filing cabinet in the PI's office. Nearly all of the data will be collected electronically by either entering it in Qualtrics or collected through the TWM intervention website. That data will be stored on a secure password protected UMN server.

Data are collected and stored on University of Minnesota servers. Identifying information are separated from their data into distinct tables. Participant information is stored at the time of enrollment and identification numbers are generated by computer. Only the PI, project statistician and project coordinator have access to this identifying information, protected in a password-protected database. All data stored within computer files will be password protected behind a firewall to ensure that access is available only to those directly involved in the study analysis. Only data that has been stripped of all personal identifying information is made available to study investigators. At study completion, the link between the identifying

information and their data is destroyed, as is contact information. Two sets of the cleaned data set will be maintained—one working copy at the University of Minnesota computer system and one on a password protected drive stored in a locked filing cabinet. This approach ensures that the data survives in the event of failure of the computer system. Finally, all study investigators and staff will have completed the CITI Course in the Protection of Human Research Subjects online training in research ethics to ensure that all staff are compliant with confidentiality training.

Data collected from surveys, blood draws for VL, and urine screens will be entered into Qualtrics. Qualtrics is the preferred survey and screening tool for the University of Minnesota because it "meets stringent information security requirements" including a password protected log-in based on our institution's x500 system. Participants will be assigned a user ID upon enrollment. Enrollment data with identifying information will be de-coupled from survey responses and records of VL and substance use. The TWM website will use an https URL and entry into the website is also password protected.

## **19.0 Provisions to Monitor the Data to Ensure the Safety of Participants**

The PI is responsible for monitoring adverse events occurring during the study. In the event the PI is unavailable, [name] has overall responsibility during his absence. The role of the person responsible is to: 1) to identify the concern, 2) activate an appropriate response (consulting where ever possible) to minimize the adverse event, and 3) ensure the adverse event is reported to the responsible authority in a timely manner.

Anticipated adverse events: In this behavioral research, the risks as a result of participation are considered minimal and primarily involve a) emotional discomfort due to the sensitive nature of the questions asked in the surveys and the information presented, as well as the features available in the intervention, b) the potential for hostile interactions with other participants, c) obtaining inaccurate information about adherence from other participants, and d) the risk of loss of confidentiality. Because this study includes individuals living with HIV/AIDS, there is also the potential for a participant to become physically ill during participation at the study site.

Emotional discomfort: Emotional discomfort may be identified in two ways. First, participants may directly correspond with project staff and report emotional discomfort. Second, emotional distress may be identified through daily monitoring of user-generated content during the intervention. To address the risk of participant distress, all

PROTOCOL TITLE: A Technology-Delivered Peer-to-Peer Support ART Adherence

Intervention for Substance-using HIV+ Adults

VERSION DATE: 4/2/18

participants are given information on how to contact the PI, the project coordinator, and the human subjects protection program. Situations in which emotional distress is noted through daily monitoring, study staff will contact the participant directly via e-mail and/or telephone. If such contact is made, the PI or project coordinator will assess the degree of emotional discomfort and either reassure the participant or provide resource information to locate a mental health provider for counseling. The PI and project coordinator will be available at any point to assist with locating an appropriate mental health provider. When indicated, the investigator will ask for permission to phone the participant at an appropriate follow-up time (e.g., the next day) to ensure any potential adverse event is followed-up adequately. If the project coordinator is handling the matter, he is responsible for informing the PI as soon as logistically possible that an adverse event may have occurred. All reasonable steps will be taken to ensure that the participant's confidentiality is protected while attempting to facilitate the appropriate level of care.

Hostile interactions: We will use the daily monitoring as an opportunity to flag hostile interactions between participants. Hostile interactions between participants will be handled by, first, reminding the participants in the interaction of the "group rules" regarding appropriate interactions. If the hostility continues, the offending participants will be given a warning that the continued hostility will result in withdrawal from the study if it continues. On the third offense, the offending participant will be withdrawn from the study. Text containing hostile exchanges will be removed from the study website and unavailable to view.

Inaccurate adherence information: We have established a daily monitoring protocol to review user-created content for inaccurate adherence information (in addition to emotional discomfort arising from hostile interactions or intervention activities). In cases in which inaccurate information is found in the forums, project staff will post a comment on the forum that provides accurate information on the topic.

Risk of loss of confidentiality: The protections against loss of confidentiality have been summarized in the protection against risks section above. The PI is the person primarily responsible for ensuring that no loss of confidentiality occurs. Any loss of confidentiality that occurs despite these protections will be dealt with on a case-by-case basis. We would expect to hear about any loss of confidentiality in one of the following ways:

PROTOCOL TITLE: A Technology-Delivered Peer-to-Peer Support ART Adherence

Intervention for Substance-using HIV+ Adults

VERSION DATE: 4/2/18

- Loss of confidentiality secondary to attempt to subpoena. Should someone attempt to subpoena our data, the PI will immediately activate our emergency response protocol. This protocol includes informing the university attorneys, our IRB office, and the project officer at NIH, that a legal attempt is being made to subpoena a person's data. In the first instance, the PI is responsible for seeking legal advice on how to respond to the request. Where a specific participant is named, the PI shall ask the NIH project officer, our IRB, and our legal advisor whether or not to inform the subject that an attempt to subpoena his data has been made.
- Loss of confidentiality secondary to theft, hacking or other illegal activity. During the course of the study, if we discover that despite security precautions our computer system has been hacked, or if someone has illegally gained access to any data, then the PI will try to determine to what extent the hacking has been successful. The investigator is responsible for informing the President's office, the University of Minnesota attorneys, our IRB, the NIH project officer, and, if deemed appropriate, our police department. The PI, in consultation with the above persons, is responsible for determining what action, if any, is appropriate. It is anticipated that in the unlikely event such an action occurred, we would first attempt to contact every subject to inform them that their data may have been hacked, and second, where a person or agency is suspected of having illegally gained access to confidential materials, to seek legal recourse to prevent further use or distribution of the data. Upon reasonable suspicion that our database has been hacked, all data collection shall be suspended until such time that the incident has been reviewed and a secure mechanism of continuing to obtain and store data has been re-established.
- Death occurring during the study. AIDS, by definition is a life-threatening condition. We may anticipate some loss to follow-up due to death. We expect notification of death to come primarily when all attempts to contact the participant have failed, and we call their contact person. In such cases, we will identify ourselves as "calling from the Hunter College, trying to locate <<person's name>> in regard to a study we are conducting." Requests for information about the study will be politely declined since they could constitute a threat to confidentiality. Where contacts report a participant has died, it will be our practice to express our sympathies to the person, thank them for providing the information, and to terminate the call, as soon as propriety allows. While IRB requirements for clinical studies include to report all deaths during a study, such requirement do not pertain to the evaluation of behaviorally-based Internet-based interventions.

Hence, we will seek permission from our IRB not to report deaths occurring during the follow-up phase of the study, but instead to log these as natural events to be reported at the end of the study.

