Substance Use. Information on substance use was collected in two-ways at each assessment time point: urinalysis and self-report. First, participants completed urine screens to detect for the following substances using the Integrated E-Z Split Key Cupp II-5 panel (Innovacon Laboratories): THC (marijuana), methamphetamine, amphetamine, cocaine, and opioids. This test is able to detect for methamphetamine, amphetamine, cocaine, and opioids from 1 to 4 days after use and THC (marijuana) for up to 30 days after use. For this analysis, positive urinalysis is defined as any detectable measure of methamphetamine, amphetamine, cocaine or opioids. Finally, alcohol use was assessed using the Alcohol Use Disorders Identification Test (AUDIT).(7)

Statistical Analyses.

Descriptive statistics (means [sd], frequencies [%]) were generated to describe the participants in the *TWM* study. Appropriate statistical tests were used to compare numeric (t-test) and categorical variables (chi-square) between the *TWM* intervention and control arms at baseline. All analyses were conducted using STATA v14 and significance was established at $p < 0.05$.

In order to account for missing data during follow-up, multiple imputation was utilized. Demographic, psychosocial, and substance-use factors that were associated with having a detectable HIV-1 VL baseline were used to impute missing variables at subsequent time points and detectable viral loads at month-5, month-11, and month-17 follow-ups. We utilized Generalized Estimating Equations to assess the *TWM* intervention over time using the binomial family and an independent correlation structure on undetectable VL over follow-up in an unadjusted model, a model adjusted for baseline differences, and stratified by urinalysis at baseline (positive vs negative drug users). The main effects of interest are the condition-by-time interaction terms at Month-5, Month-11, and Month-17. These represent the differences-in-

differences in proportion of those with an undetectable VL between participants in the *TWM* intervention arm and those in the control arm.

References

1. Radloff LS. The CES-D scale: A self-report depression scale for research in the general population. *Applied Psycholgical Measurement*. 1992;1:385-401.
2. The LifeWindows Project Team. The LifeWindows Information Motivation Behavioral Skills ART Adherence Questionnaire (LW-IMB-AAQ). 2006.

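### The protocol would ask the IRB to let follow-up deaths go unreported until study end under a natural-event label, and the SAP has no rule against imputing viral load after death

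*Protocol*

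**What the plan says.** **Reporting.** Protocol Section 19.0 opens with a general duty: "The PI is responsible for monitoring adverse events occurring during the study". One of the listed tasks is to "ensure the adverse event is reported to the responsible authority in a timely manner". No exception for death is made there. The paragraph on deaths later in the section announces a request to the IRB for leave "not to report deaths occurring during the follow-up phase of the study, but instead to log these as natural events"; the log would be handed over only when the study closes. The reason given is that, for IRB reporting of deaths, "such requirement do not pertain to the evaluation of behaviorally-based Internet-based interventions". When a contact person tells staff that a participant has died, the procedure is to offer sympathy, thank the person and end the call. Nothing asks for the date or cause of death, or for a judgement of relatedness.

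**Analysis.** The same paragraph treats death as a form of attrition: "We may anticipate some loss to follow-up due to death". The SAP, under Statistical Analyses, says: "In order to account for missing data during follow-up, multiple imputation was utilized", and it names detectable viral load at months 5, 11 and 17 among the imputed variables. The SAP does not mention death. Protocol Section 17.1 differs: it reserves multiple imputation for covariates and leaves missing outcomes to the mixed model. It has no rule for death either.

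**The concern.** These are two separate problems that meet at the same event.

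The first is oversight. A label of natural event is fixed before any cause is known, and the procedure offers no route to learning it. Half the sample is to be recent illicit drug users (Section 5.1), depressive symptoms are measured (Section 3.3), and emotional discomfort is an anticipated adverse event (Section 19.0). An overdose or a suicide could therefore be logged in the same way as any other death. On the SAP's visit schedule, follow-up after the 5-month intervention runs 17 - 5 = 12 months, most of a man's time in the trial. No independent monitoring board is described, so the IRB is the main outside body that could notice a pattern.

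The second is the meaning of the primary outcome. Viral load after death does not exist, so an imputed value answers a hypothetical question that the plan never states. Some men who died would be counted as undetectable, and a difference in mortality between arms would not show in the primary result.

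**Working it through.** **Reporting: the passages side by side.**

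- General duty in Section 19.0: timely report to the responsible authority, with no carve-out for death.
- Death paragraph in Section 19.0: request not to report in the follow-up phase, with a log reported at study end.
- Subpoena and hacking paragraphs in Section 19.0: the IRB and the NIH project officer are informed.
- Reason given: the trial is behavioural and Internet-based. Yet Sections 3.3 and 5.2 describe blood draws at in-person visits, and Section 14.1 lists infection from phlebotomy as a risk.

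The death paragraph can be read as a specific exception to the general duty, but the section does not say so. Follow-up phase is not defined.

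**Analysis: inputs.** From protocol Section 17.2: 200 men per arm, 60% undetectable in the intervention arm and 46% in the control arm at 5 months. From the SAP: significance at 0.05, taken here as two-sided. Assumed, because the documents give no figure: 80% power as the target; 1% to 3% deaths per arm by month 17 (2 to 6 of 200); the month-5 rates carried forward to survivors at later visits; imputed values that average the survivors' rate in the same arm.

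**The plan's own figure.** With pooled variance and no continuity correction,

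z = [0.14 × √200 - 1.96 × √(2 × 0.53 × 0.47)] / √(0.60 × 0.40 + 0.46 × 0.54) = (1.980 - 1.383) / 0.699 = 0.85,

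which is 80.3% power. The smallest detectable difference from 60% at 80% power is 13.9 points, so the stated 14 points reproduces.

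**Effect of the rule for death.** Imputing at survivors' rates leaves the expected difference at 60 - 46 = 14.0 points. Counting deaths as not undetectable gives 0.60 × (1 - dI) - 0.46 × (1 - dC), where dI and dC are the proportions dead in the intervention and control arms. The change is therefore 0.46 × dC - 0.60 × dI.

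| Deaths, intervention v control (of 200) | Intervention | Control | Difference | Change (points) |
|---|---|---|---|---|
| 2 v 2 | 59.40% | 45.54% | 13.86 | -0.14 |
| 6 v 6 | 58.20% | 44.62% | 13.58 | -0.42 |
| 2 v 6 | 59.40% | 44.62% | 14.78 | +0.78 |
| 6 v 2 | 58.20% | 45.54% | 12.66 | -1.34 |

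The change is positive only when control deaths exceed 0.60 / 0.46 = 1.30 times intervention deaths. Deaths occur after baseline, so the shift in the SAP's difference-in-differences is the same if that effect is expressed as a difference in proportions.

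**Men affected.** The expected number of deaths imputed as undetectable is 2 × 0.46 = 0.9 to 6 × 0.60 = 3.6 per arm. Power with deaths counted as not undetectable is 79.5% for 2 v 2, 84.4% for 2 v 6 and 71.9% for 6 v 2.

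**The case against.** On reporting, the strongest reply is that the text is a request, not a decision. The IRB would have to agree, and the documents do not show that it did. The request covers only the follow-up phase, so no waiver is sought for deaths during the intervention. Monitoring by the investigator continues throughout. A specific exception with a stated reason is also not a plain contradiction of a general duty, and natural event may be loose wording rather than a ruling on cause. All of this stands as a limit on the point. A reader might infer that deaths will be withheld from the IRB or that there will be no timely safety review; the documents support neither. What remains is that, if permission were granted, IRB notice of follow-up deaths would be late and the log would lack what is needed to judge them.

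On analysis, the SAP never says that deaths are imputed. That follows only from joining the protocol's attrition sentence to a SAP sentence with no exception, and Section 17.1 confines imputation to covariates. This too stands: the defect is silence, so men who died may, not will, receive imputed values. Section 17.1 does not remove the gap, because its mixed model also makes no distinction between death and dropout.

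A reader might also infer that most deaths would be imputed as undetectable, or that the result is tilted towards the intervention. The first fails at the control planning rate of 46%, and the imputation model uses baseline factors that vary from man to man. The second fails because the direction depends on which arm loses more men.

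Finally, counting death as not undetectable is one choice of estimand among several, and nothing in the documents requires it. That is fair. The firm request is that the SAP state a rule and not impute after death.

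**Conclusion.** The point holds as two limited gaps. First, Section 19.0 seeks to defer IRB reporting of follow-up deaths and classes them in advance, with no step to record date, cause or relatedness; this must be reconciled with the timely-reporting duty in the same section. Second, the SAP has no rule for viral load after death, and its imputation as written could supply values for men who died.

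The first gap carries more weight. The second is mainly a matter of definition: under the assumed 1% to 3% mortality and the planning rates, the 14-point difference moves by 0.1 to 0.4 points downward if deaths are balanced, and by +0.8 or -1.3 points for a 1% v 3% split. These sizes rest on assumed death rates and would grow with more deaths or a larger imbalance. The change is worth making because it is cheap, not because the primary result is likely to turn on it.

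**What to change.** **Protocol Section 19.0.** Remove the request to defer and the automatic natural-event label. Report each death to the IRB when it is learned of, with date, arm and cause where known, and add a step for recording these and for judging relatedness. The call procedure can still protect confidentiality.

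**SAP.** Tabulate deaths by arm and by visit interval. State that viral load is not imputed at visits after death. One workable rule counts those visits as not undetectable in the primary analysis, with a sensitivity analysis that leaves them out. With the independence working correlation already chosen, leaving them out describes men alive at each visit. Imputation then applies only to men not known to have died. Say also that this replaces the missing-data text in protocol Section 17.1.

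**Cost.** A few IRB reports, one small table and a few SAP sentences. The estimate may move slightly in either direction. The SAP is dated after the protocol's planned study end, so if follow-up has closed, the reporting part reduces to completing the death log with arm, date and known cause and reporting it; the SAP part is unaffected.
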